13 STATISTICAL CONSIDERATIONS

A Statistical Analysis Plan (SAP) will be finalized before database lock and conduct of the final analysis is undertaken. The main features of the planned statistical analysis are included below.

13.1 Sample Size

The primary analysis of response rate will take place when 44 patients are enrolled at the selected dose and all active patients have undergone the required assessments for assessment of confirmed ORR by RECIST. The study will be considered to have met its primary endpoint if a minimum of 4 confirmed responses (CR or PR) is observed. Based on 44 patients, if the true ORR is 15%, there is greater than an 80% probability of observing 4 or more responses. Furthermore, if the true response rate were only 5%, there would be less than a 7% probability of observing 4 or more responses.

Upon review of the data from Part II by the DSMC, the study may be further expanded at the selected dose level, which will be described in a protocol amendment.

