Study Treatment:	Eligible consenting patients will receive NUC-1031 by intravenous (IV) infusion over 30 minutes at a dose of 500 mg/m ² or 750 mg/m ² on days 1, 8 and 15 of a 28-day schedule. Protocol-specific guidelines for dose modifications and discontinuations due to adverse events are provided. Patients will continue to receive NUC-1031 until the occurrence of disease progression using RECIST or unmanageable drug-related adverse events despite dose modification.

Sample Size:	
Two dose levels of NUC-1031, 500 mg/m² and 750 mg/m², will be evaluated in parallel cohorts of up to 20 patients each in Part I of the study. One dose level will be selected for further evaluation in Part II of the study (based on ongoing safety, dosing intensity, PK and clinical activity observed during Part I), where enrollment shall continue until a total of 44 evaluable patients are recruited at the selected dose. The primary objective will be assessed in these 44 patients.
 
The study will be considered to have met its primary endpoint if a minimum of 4 responses (CR or PR) are observed. Based on 44 patients, if the true ORR is 15%, there is greater than an 80% probability of observing 4 or more responses. Furthermore, if the true response rate were only 5%, there would be less than a 7% probability of observing 4 or more responses.
 
Data dependent, an efficacy update analysis may also be performed to provide more mature efficacy data, particularly for the longer term efficacy endpoints such as DOR, PFS and OS. The need for such an analysis, and its timing, will be determined by the DSMC following review of the primary analysis results.
 
Upon review of the primary analysis data from Part II by the DSMC, the study may be further expanded at the selected dose level, which will be described in a protocol amendment.

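### The success rule of 4 or more responses in 44 has a 17.7% false-positive probability at a 5% response rate, not below 7%; only a threshold of 5 meets both stated figures

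*Protocol*

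**What the plan says.** Section 13.1 of the protocol sets the sample size and the decision rule for the primary endpoint, confirmed objective response by blinded independent central review at the selected dose.

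- Timing and number: "The primary analysis of response rate will take place when 44 patients are enrolled at the selected dose". The Sample Size entry of the synopsis confirms the denominator: "The primary objective will be assessed in these 44 patients".
- Success rule: "The study will be considered to have met its primary endpoint if a minimum of 4 confirmed responses (CR or PR) is observed".
- Stated power: "Based on 44 patients, if the true ORR is 15%, there is greater than an 80% probability of observing 4 or more responses".
- Stated false-positive probability: "if the true response rate were only 5%, there would be less than a 7% probability of observing 4 or more responses".

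The synopsis gives the same rule, without the word confirmed ("The study will be considered to have met its primary endpoint if a minimum of 4 responses (CR or PR) are observed"), and repeats both probabilities. The protocol gives no other threshold or error rate for the primary endpoint.

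**The concern.** The rule and its two operating characteristics are fully specified: a number of patients, a minimum number of responses and two true response rates. They can therefore be checked exactly. In 44 patients a 5% response rate gives 44 × 0.05 = 2.2 expected responses, so seeing 4 or more cannot be rare. A probability below 7% looks too small.

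This is the protocol's only success criterion for the primary endpoint. If the stated error rate is wrong, anyone who judged the design by it, including ethics committees, regulators and the DSMC, has been told that an insufficiently active dose is much less likely to pass than it really is. There is also a practical ambiguity. A trial that ends with exactly 4 responses succeeds under the written rule but fails under the rule that matches the printed probabilities. The DSMC's review of these data may lead to expansion of the study, so the classification has consequences.

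**Working it through.** **Inputs, all from Section 13.1 and repeated in the synopsis**

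- n = 44 patients at the selected dose
- success if the number of responders X is at least r, with r = 4
- uninteresting response rate 5%, stated P(X ≥ 4) below 7%
- target response rate 15%, stated P(X ≥ 4) above 80%

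**Formula.** X ~ Binomial(44, p), and P(X ≥ r) = 1 − Σ C(44, k) p^k (1 − p)^(44 − k), summed over k = 0 to r − 1.

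**Step 1: attempt to reproduce the stated 7% (p = 0.05, r = 4)**

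| k | P(X = k) |
|---|---|
| 0 | 0.1047 |
| 1 | 0.2424 |
| 2 | 0.2743 |
| 3 | 0.2021 |
| Sum | 0.8235 |

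P(X ≥ 4) = 1 − 0.8235 = 0.1765. The stated figure is not reproduced. Against the stated ceiling the ratio is 17.65 / 7 = 2.5.

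**Step 2: the 15% statement (p = 0.15, r = 4)**

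P(X ≤ 3) = 0.0008 + 0.0061 + 0.0231 + 0.0571 = 0.0871, so P(X ≥ 4) = 0.9129. The statement of more than 80% is true, but it understates the power by about 11 points.

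**Step 3: neighbouring thresholds, n = 44**

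| Minimum responses | P at 5% | P at 15% | Below 7%? | Above 80%? |
|---|---|---|---|---|
| 3 | 37.9% | 97.0% | no | yes |
| 4 (as written) | 17.65% | 91.3% | no | yes |
| 5 | 6.75% | 80.97% | yes | yes |
| 6 | 2.16% | 66.4% | yes | no |

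Moving from 4 to 5 removes P(X = 4), which is 0.1090 at p = 0.05: 0.1765 − 0.1090 = 0.0675. Only a threshold of 5 meets both bounds, and it sits just inside each of them.

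**Step 4: could another method or input give a figure below 7% with r = 4?**

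- Approximations at p = 0.05, n = 44: Poisson 18.1%, normal with continuity correction 18.4%, normal without correction 10.7%. None is below 7%.
- Keeping n = 44 and r = 4, the probability is below 7% only if the true response rate is below about 3.5%.
- Keeping r = 4 and 5%, it is below 7% only for n of 31 or fewer. At n = 31 it is 6.71%, but power at 15% is then 70.4%, which breaks the other statement.

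**The case against.** The arithmetic cannot be defended as written. The protocol states the figure itself, twice, so the error is not a detail left to the SAP and not an artefact of a broken table. The fair objections concern how much follows from it.

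- **Only one of the two probabilities is false.** The 15% statement holds at a threshold of 4. This stands, and the finding is limited to the 5% statement.
- **The protocol does not show which element is the mistake.** The number 4 is used consistently in both places, so the sponsor may have meant 4 and attached the wrong probabilities. The close fit of both figures to a threshold of 5 suggests that more than 4 was written as 4 or more, but this is an inference. This stands too, and the choice belongs to the sponsor.
- **A confidence-interval argument would not help.** The exact 95% interval for 4/44 is 2.5% to 21.7% and includes 5%, but the interval for 5/44 is 3.8% to 24.6% and also includes 5%. The protocol does not require the interval to exclude 5%. The point therefore rests on the tail probability alone.
- **No formal hypothesis test is stated, and any expansion goes through DSMC review and an amendment.** This softens the consequences of a false success. It does not make the printed error rate correct, and the rule remains the only stated criterion for success.

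**Conclusion.** The concern holds. Under the written rule, a dose with a true response rate of 5% would be declared successful 17.65% of the time, against a stated probability below 7%. Power at 15% is 91.3%. A threshold of 5 yields 6.75% and 80.97% and is the only threshold in 44 patients consistent with both stated figures.

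The calculation assumes a single fixed-size evaluation of 44 independent patients with a common response probability, which is how the protocol presents it. Part I patients at the selected dose count towards the 44, and that dose is chosen partly on clinical activity, so the actual false-positive probability would tend to be somewhat higher than the binomial figure. That is a separate matter and does not alter this conclusion.

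The error must be corrected, because it concerns the sole decision rule for the primary endpoint.

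**What to change.** Correct Section 13.1 and the Sample Size entry of the synopsis together, in one of two ways.

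1. **Change the threshold to 5.** Success requires at least 5 confirmed responses by central review among the 44, and both probability statements refer to 5 or more. The stated figures then hold (81.0% at 15%, 6.7% at 5%).
2. **Keep the threshold at 4.** Restate the probabilities as about 91% at a true rate of 15% and about 18% at 5%, and accept that false-positive level openly.

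In either case, add confirmed to the synopsis rule so that it matches Section 13.1.

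Neither option needs more patients. Option 1 lowers power from 91% to the 81% that the protocol already implies. It also changes the success criterion, so it needs an amendment with the approvals that Section 15.4 requires. Option 2 leaves the criterion alone and corrects only the description of its properties, although that text change also goes through Section 15.4. The study is open-label, so the amendment should record what response data had been seen when the choice was made. The choice should be settled before the primary response results are known.

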13.2 Missing, Unused and Spurious Data

All available safety, PK, and efficacy data will be included in tabulations and patient-level listings. No imputation of values for missing data will be performed.

13.3 Analysis Populations

The analysis of time to progression, PFS, OS and health-related quality of life (HRQoL) data will be summarized and analyzed in all patients enrolled, regardless of treatment received (the full analysis set, FAS) on an intention-to-treat (ITT) basis.

The primary analysis of response rate will be based on a blinded independent central review (BICR) of confirmed response rate by RECIST. Only patients with measurable disease at baseline (defined by BICR) will be included in the Evaluable for Response population. This population will be analyzed for all related response measurements. Sensitivity analyses will be performed including using the investigator-recorded assessment. For the purposes of dose selection, unconfirmed responses will be taken into account but for all other analyses confirmation of response is required.

As warranted by the data, efficacy may also be assessed in sub-populations, as defined by NuCana prior to database lock. Any sub-group analyses will be exploratory and their purpose would be to assess consistency of treatment effect across potential or expected prognostic factors, or biomarkers. Analyses will not be performed if there are too few events available for a meaningful analysis of a particular sub-group.

For the assessment of safety and tolerability, summaries will be produced based on the Safety Analysis Set. This will include all patients who receive at least one dose of study treatment.

PK analyses will be performed on the PK population, defined as all patients who receive any amount of NUC-1031 and have sufficient data for PK analysis.

13.4 Patient Disposition

Data tabulations will summarize the following patient numbers:

- Enrolled
- At least one dose of NUC-1031 received
- Evaluable for safety and efficacy
- Protocol violations
- Withdrew from study due to:
 - AE
 - Investigator request
 - Withdrew consent
 - Lost to follow-up
 - Other reasons, as collected in the CRF.

13.5 Statistical Methods

13.5.1 Demographics and Baseline Data

Demographic and baseline characteristics of patients will be summarized using descriptive statistics:

- Age
- Sex
- Race
- Ethnicity
- Baseline ECOG performance score
- Primary diagnosis
- Disease stage at diagnosis and baseline
- Prior therapies, including systemic therapies, radiation, and surgeries
- Other baseline characteristics, as collected in the CRF.

13.5.2 Concomitant Medications

The number and proportion of patients in the Safety analysis set using different concomitant medications will be tabulated and summarized by WHO DD anatomical, therapeutic, chemical class and preferred term.

Use of hematopoietic growth factors and transfusions are of special interest.

13.5.3 Extent of Exposure

Descriptive statistics for patients treated, including the number of infusions received, total dose given, and infusions delayed or missed, will be presented.

13.5.4 Efficacy Analysis

The primary response evaluation is based upon the determination of response using RECIST ([Appendix 2](#)) by a BICR:

- **ORR** is defined as the number of patients achieving a confirmed response (CR or PR). Number and percentage of patients achieving a response, with confidence intervals, will be provided. In addition, the number and percentage of patients achieving individual best response criteria of CR, PR, SD, PD, or NE will be described.
- **Change from baseline in tumor size** is measured as the percentage change in the total measurements of target lesions from the pre-treatment scan, measured at each scheduled scan.
- **Duration of Overall Response** is measured from the time measurement criteria are first met for CR or PR (whichever is first recorded) until the first date that recurrent or PD is objectively documented (taking as reference for PD the smallest measurements recorded since the treatment started). Only responses that were later confirmed, will be considered when calculating the DoR. For patients who were lost to follow-up without progression or reached the time point of analysis without a known record of death or progression, the duration of response will be censored at the date of last tumor assessment.
- **PFS** is defined as the time from the date of study treatment initiation (start of treatment) to the first date of objectively determined PD or death from any cause. For patients who are still alive at the time of the data cut-off date and without evidence of tumor progression, PFS will be censored at the date of the most recent objective progression-free observation. For patients who receive subsequent anticancer therapy prior to objective disease progression or death, PFS will be censored at the date of the last objective progression-free observation prior to the date of subsequent therapy.

The number of overall censored patients, number of patients with events and Kaplan-Meier estimates median time will be provided. In addition, the results will be presented graphically in Kaplan-Meier plots.

- **Time to Disease Progression** is measured from the start of the treatment until the criteria for progression are first met, taking as reference the smallest measurements recorded since the treatment started, including the baseline measurements. For patients who were lost to follow-up, or died without progression or reached the time point of analysis without a known record of progression, the time to progression will be censored at the date of last tumor assessment.

The number of overall censored patients, number of patients with events and Kaplan-Meier estimates median time will be provided. The results will also be presented graphically in Kaplan-Meier plots.

- **Disease Control Rate** is defined as the number of patients achieving confirmed response (CR or PR) or SD as best overall response (as defined in RECIST).
- **Best GCIG Overall Response** (CR, PR, SD, PD, NE): number and percentage of patients with responses defined per GCIG criteria will be described.
- **OS** is defined as the time from randomization until death from any cause. All deaths will be included, whether they occur during the study or following treatment discontinuation. For patients who have not died, overall survival will be censored at the date of last contact.

The number of overall censored patients, number of patients with events and Kaplan-Meier estimates median time will be provided. In addition, the results will be presented graphically in Kaplan-Meier plots.

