3 INVESTIGATIONAL PLAN

3.1 Overall Study Design

This is a randomized open-label, two-part clinical study of NUC-1031 in up to 64 patients with platinum-resistant ovarian cancer. Patients will be randomized to NUC-1031 500 mg/m² or 750 mg/m² and will be evaluated in two parallel cohorts of up to 20 patients each in Part I of the study. The randomization will be stratified to ensure that key prognostic markers, including BRCA mutation status and number of prior lines of chemotherapy (3 or >3), are balanced between the 2 dose levels. The stratification procedure will be defined in the statistical analysis plan.

On the basis of ongoing safety, dosing intensity, PK and clinical activity observed during Part I, one dose level will be selected for further evaluation in Part II of the study, where enrollment shall continue until a total of 44 response evaluable patients are recruited at the selected dose (Figure 1).

[figure not shown]

Figure 1 PRO-105 Study Schema

The primary analysis of response rate will take place when 44 patients are enrolled at the selected dose and all active patients have undergone the required assessments for assessment of confirmed ORR by RECIST (*i.e.*, approximately 16 weeks after the 44th patient starts treatment). Upon review of these data from Part II by the DSMC, the study may be further expanded at the selected dose level, which will be described in a protocol amendment. An efficacy update analysis may also be performed to provide more mature efficacy data.

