3.3 Study Treatment

In Part I, eligible consenting patients will be randomized to receive IV NUC-1031 at a dose of either 500 mg/m² or 750 mg/m² on a day 1, 8 and 15 of a 28-day schedule. Up to 20 patients will be enrolled in each arm.

One dose level will be selected for further evaluation in Part II of the study (based on ongoing safety, dosing intensity, PK and clinical activity observed during Part I), where enrollment shall continue until a total of 44 evaluable patients are recruited at the selected dose. The study will be complete when all patients have reached the PFS endpoint or when 24 months have elapsed since the final patient was enrolled (whichever comes first).

Criteria for inter-cycle and intra-cycle dose delay and dose modification are specified in [Section 9](#) of this protocol. The reasons for dose delay or dose reduction should be captured as AEs in the patient medical record and noted on the case report form (CRF).

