5.2 Patient Registration and Screening Procedures

All screening activities must be performed within 28 days of randomization. A Screening Log must be kept of all patients considered for the study (*i.e.* all those that are included for screening and any that are subsequently excluded). The reason for exclusion must be recorded on this form. A copy of the Screening Log must be retained on site and provided to the CRO upon request, but without patient identifiers.

In Part I, patient randomization will be stratified according to BRCA mutation status and number of prior lines of chemotherapy (3 or ≥ 3). In Part II, sensitivity analyses will be conducted of efficacy endpoints according to BRCA mutation status. Patients known to have germline BRCA mutation(s) prior to randomization can enter the study based on this result. Patients who have had a tumor BRCA mutation identified in a certified laboratory may also be enrolled on the study based on this result. Patients with unknown BRCA mutation status should undergo local BRCA mutation testing prior to study entry, according to local ethical procedures for genetic testing.

Before entering a patient onto the study, the Medical Monitor, in consultation with the Sponsor, will confirm eligibility according to the defined inclusion and exclusion criteria. Details of the query and outcome of the decision must be documented on the registration/ eligibility checklist. To register a patient to the study, the site must email a completed Registration Form, along with a copy of the blinded histology report, to the patient registration email address supplied. The site will be informed by email and fax of the approval to be treated. Treatment must not start until this registration process is complete and must start no later than 10 days after the day of registration.

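### OS is timed from randomization, which is described only for Part I, and survival calls omit patients who start new therapy before RECIST progression

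*Protocol*

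**What the plan says.** **Start of the OS clock.** Section 13.5.4 states that OS "is defined as the time from randomization until death from any cause". Section 13.3 places OS in "all patients enrolled, regardless of treatment received (the full analysis set, FAS"). PFS and time to progression, by contrast, run from the start of treatment.

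**Where randomization occurs.** Section 3.3: "In Part I, eligible consenting patients will be randomized to receive IV NUC-1031" at one of two doses. Section 5.2: "In Part I, patient randomization will be stratified according to BRCA mutation status" and prior lines of chemotherapy. For Part II, Section 3.1 says that one dose is selected, "where enrollment shall continue until a total of 44 response evaluable patients are recruited at the selected dose"; no randomization step is described. Section 5.2 also uses the word without naming a Part: "All screening activities must be performed within 28 days of randomization". The baseline imaging window and the timing of BRCA results use it in the same way.

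**Survival follow-up.** Section 5.5.8 and footnote 23 of the Summary Schedule of Events give 12-weekly phone calls to patients with RECIST-defined progression, in order to determine OS. Patients who stop treatment without progression are followed every 8 weeks instead. Section 13.5.4 then adds: "For patients who have not died, overall survival will be censored at the date of last contact".

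**The concern.** An endpoint analysed in all enrolled patients needs a start date that all of them have. As written, the OS clock can be applied to Part II patients only by putting some other date in place of randomization, and the protocol does not say which.

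The second problem lies in data collection. OS is meant to include every death, but the only contact scheduled for the purpose of OS depends on a RECIST event. A patient whose tumour follow-up ends for another reason falls between the two schedules. If a change of therapy is what removed the patient, censoring at last contact may be related to prognosis. No later analysis plan can recover survival status that was never collected. The protocol synopsis also names OS among the endpoints for which a later, more mature efficacy update may be run, so the completeness of follow-up matters.

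**Working it through.** **1. Reproducing the plan's total.** Inputs: up to 20 patients per dose in Part I, and 44 response-evaluable patients at the selected dose (Section 3.1).

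- Part II patients at the selected dose: 44 − 20 = 24.
- Maximum enrolled: 20 + 20 + 24 = 64, which matches the stated maximum of 64.

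**2. Patients with no described OS start date.** Let *a* be the number of Part I patients at the selected dose who count towards the 44, with *a* ≤ 20. The number entering in Part II is 44 − *a*. The last column assumes *a* patients in each Part I arm.

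| *a* | Part II patients | Share of 44 | Share of all enrolled, (44 − *a*)/(44 + *a*) |
|---|---|---|---|
| 20 (plan maximum) | 24 | 24/44 = 54.5% | 24/64 = 37.5% |
| 15 (assumed) | 29 | 29/44 = 65.9% | 29/59 = 49.2% |
| 10 (assumed) | 34 | 34/44 = 77.3% | 34/54 = 63.0% |

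The 44 are response-evaluable patients, whereas OS uses all enrolled. If *N* > 44 are enrolled at the selected dose and Part I is still capped at 20, the share (*N* − 20)/*N* exceeds 54.5%. So 54.5% is a minimum.

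**3. How far the clock could move.**

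- Section 5.2 says that treatment "must start no later than 10 days after the day of registration". Registration and first dose therefore differ by at most 10/30.44 = 0.33 month.
- For Part I patients, Appendix 2 allows baseline evaluations no more than 4 weeks before treatment. If the scan showing measurable disease precedes randomization, randomization to first dose is at most 28/30.44 = 0.92 month. That ordering is inferred from the eligibility rules.

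The plausible start dates therefore lie days to a few weeks apart.

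**4. Survival contact.** Take a patient who stops NUC-1031 without RECIST progression and then starts another therapy.

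| Provision | Does it end 8-weekly follow-up at a new treatment? |
|---|---|
| Section 3.4 | Yes |
| Section 5.5.6 (heading) | Yes |
| Section 6.2 | Yes |
| Schedule footnote 21 | Yes |
| Section 5.5.8 | Not listed as a stop |
| Section 11.1 | Not listed as a stop |

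Under the first four, follow-up ends when the new therapy starts. The calls in Section 5.5.8 and footnote 23 never start, because they require RECIST progression. No survival contact remains scheduled, and OS is censored at last contact unless a death becomes known by another route. Under Sections 5.5.8 and 11.1, scans would run on to progression and the calls would then begin.

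The protocol expects such patients. Section 6.1 lists reasons to stop that need no RECIST progression, and the PFS definition has a censoring rule for those who receive another anticancer therapy first. How many there will be is not stated and cannot be derived.

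**The case against.** The strongest reply on the clock is that randomization is used loosely to mean study entry, as the screening, imaging and BRCA windows suggest, and that the SAP could settle the matter in one line. This stands as a reason to expect a small numerical effect. It does not remove the error, because the protocol itself fixes the origin and defines no such date for Part II.

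On survival contact, the gap depends on which follow-up text a site applies: under Sections 5.5.8 and 11.1 a patient who changes therapy stays under assessment until progression. That is correct, and it is why the conclusion is tied to the four provisions that stop earlier. Sections 6.1, 6.2 and 11.1 also discourage stopping treatment on clinical signs alone, which should keep the group small.

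A reader might infer that patients who deteriorate without objective progression have no scheduled contact after the End of Treatment visit, because Section 12.10.1 lets the investigator forgo further disease assessments. The documents do not support this. That section concerns adverse event reporting and does not cancel visits. The schedule keeps an 8-weekly follow-up visit, and Section 6.2 asks patients who stop without progression to attend it. They are at risk only if they leave that follow-up.

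Nor should the tumour response row of the schedule be counted as a further conflict. It is shorter wording in a table whose own footnote 21 gives the new-treatment stop.

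**Conclusion.** The point holds in two parts, and should be corrected.

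- **Start date.** At least 24 of the 44 selected-dose patients (54.5%) have no described OS start date. This assumes that Part I contributes no more than 20 patients at that dose and that Part II is not randomized, which is how the protocol describes it. It is a count of patients and does not measure bias.
- **Survival contact.** Under Sections 3.4, 5.5.6 and 6.2 and footnote 21, patients who start new therapy before RECIST progression have no scheduled survival contact and are censored at last contact. The censoring may be informative; neither its extent nor its direction can be derived from the protocol. This part matters more, because the loss cannot be repaired at analysis.

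It would go too far to conclude that patients without RECIST progression are generally not followed for survival, or that the trial's main conclusion is at risk. OS is a secondary endpoint summarised by Kaplan-Meier median and plot, and the primary response rate does not depend on it.

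**What to change.** 1. In Section 13.5.4, define OS from a date that exists for every enrolled patient in both Parts, for example registration or enrolment. First dose would not serve a patient who is enrolled but never treated, whom the full analysis set includes.
2. In Section 5.5.8 and footnote 23, extend the 12-weekly survival calls to every living patient no longer attending tumour-assessment follow-up, with or without RECIST progression, who has not withdrawn consent to data collection.
3. Reconcile Sections 3.4, 5.5.6 and 6.2 and footnote 21 with Sections 5.5.8 and 11.1 on when scans stop.

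Cost: a protocol amendment, which Section 15.4 requires ethics committees and regulators to approve before use, matching SAP wording, and a few extra phone calls. Items 1 and 2 need no added visits, scans or patients. Item 3 would affect scan numbers only if the reconciled text has scans continue after a new treatment starts.
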